5.3.3. Dose and Administration

NOTE: Study treatment should begin as close as possible to the date on which the patient is enrolled.

Study treatment of pembrolizumab will be administered on Day 1 of each 21-day cycle, after all procedures and assessments have been completed as detailed in Section [6.4](#) and [Appendix D](#).

Pembrolizumab will be administered as a dose of 200 mg using a 30-minute IV infusion given approximately 60–90 minutes after administration of LV. Sites should make every effort to target infusion timing to be as close to 30 minutes as possible. However, given the variability of infusion pumps from site to site, a window between –5 minutes and +10 minutes is permitted (i.e., infusion time is 30 minutes –5 min/+10 min).

The pharmacy manual contains specific instructions for the preparation of the pembrolizumab infusion and administration of infusion solution.

5.3.4. Dose Modifications

5.3.4.1. Dose Modification and Toxicity Management for Immune-Related AEs Associated with Pembrolizumab

AEs associated with pembrolizumab exposure may represent an immunologic etiology. These irAEs may occur shortly after the first dose or several months after the last dose of pembrolizumab treatment and may affect more than one body system simultaneously. Therefore, early recognition and initiation of treatment is critical to reduce complications. Based on existing clinical study data, most irAEs were reversible and could be managed with interruptions of pembrolizumab, administration of corticosteroids and/or other supportive care. For suspected irAEs, ensure adequate evaluation to confirm etiology or exclude other causes. Additional procedures or tests such as bronchoscopy, endoscopy, skin biopsy may be included as part of the evaluation. Based on the severity of irAEs, withhold or permanently discontinue pembrolizumab and administer corticosteroids. Dose modification and toxicity management guidelines for irAEs associated with pembrolizumab are provided in [Table 15](#).

Table 15 Dose modification and toxicity management guidelines for immune-related AEs associated with pembrolizumab

General instructions:

1. Severe and life-threatening irAEs should be treated with IV corticosteroids followed by oral steroids. Other immunosuppressive treatment should begin if the irAEs are not controlled by corticosteroids.
2. Pembrolizumab must be permanently discontinued if the irAE does not resolve or the corticosteroid dose is not \leq 10 mg/day within 12 weeks of the last pembrolizumab treatment.
3. The corticosteroid taper should begin when the irAE is \leq Grade 1 and continue at least 4 weeks.
4. If pembrolizumab has been withheld, pembrolizumab may resume after the irAE decreased to \leq Grade 1 after corticosteroid taper.

Immune-related AEs	Toxicity grade or conditions (CTCAE v5.0)	Action with pembrolizumab	irAE management with corticosteroid and/or other therapies	Monitoring and follow-up
Pneumonitis	Grade 2	Withhold	Administer corticosteroids (initial dose of 1–2 mg/kg prednisone or equivalent) followed by taper	Monitor patients for signs and symptoms of pneumonitis
	Grade 3 or 4, or recurrent Grade 2	Permanently discontinue	Add prophylactic antibiotics for opportunistic infections	Evaluate patients with suspected pneumonitis with radiographic imaging and initiate corticosteroid treatment
Diarrhea/Colitis	Grade 2 or 3	Withhold	Administer corticosteroids (initial dose of 1–2 mg/kg prednisone or equivalent) followed by taper	Monitor patients for signs and symptoms of enterocolitis (i.e., diarrhea, abdominal pain, blood or mucus in stool with or without fever) and of bowel perforation (i.e., peritoneal signs and ileus).
	Recurrent Grade 3 or Grade 4	Permanently discontinue		Patients with \geq Grade 2 diarrhea suspecting colitis should consider GI consultation and performing endoscopy to rule out colitis. Patients with diarrhea/colitis should be advised to drink liberal quantities of clear fluids. If sufficient oral fluid intake is not feasible, fluid and electrolytes should be substituted via IV infusion.
AST/ALT elevation or Increased bilirubin	Grade 2 ^a	Withhold	Administer corticosteroids (initial dose of 0.5–1 mg/kg prednisone or equivalent) followed by taper	Monitor with liver function tests (consider weekly or more frequently until liver enzyme value returned to baseline or is stable)

Immune-related AEs	Toxicity grade or conditions (CTCAE v5.0)	Action with pembrolizumab	irAE management with corticosteroid and/or other therapies	Monitoring and follow-up
	Grade 3 ^b or 4 ^c	Permanently discontinue	Administer corticosteroids (initial dose of 1–2 mg/kg prednisone or equivalent) followed by taper	
Type 1 diabetes mellitus (T1DM) or Hyperglycemia	New onset T1DM or Grade 3 or 4 hyperglycemia associated with evidence of β-cell failure	Withhold ^d	Initiate insulin replacement therapy for subjects with T1DM Administer anti-hyperglycemic in subjects with hyperglycemia	Monitor subjects for hyperglycemia or other signs and symptoms of diabetes.
Hypophysitis	Grade 2	Withhold	Administer corticosteroids and initiate hormonal replacements as clinically indicated.	Monitor for signs and symptoms of hypophysitis (including hypopituitarism and adrenal insufficiency)
	Grade 3 or 4	Withhold or permanently discontinue ^d		
Hyperthyroidism	Grade 2	Continue	Treat with non-selective beta-blockers (eg, propranolol) or thionamides as appropriate	Monitor for signs and symptoms of thyroid disorders.
	Grade 3 or 4	Withhold or permanently discontinue ^d		
Hypothyroidism	Grade 2–4	Continue	Initiate thyroid replacement hormones (eg, levothyroxine or liothyronine) per standard of care	Monitor for signs and symptoms of thyroid disorders.
Nephritis: grading according to increased creatinine or acute kidney injury	Grade 2	Withhold	Administer corticosteroids (prednisone 1–2 mg/kg or equivalent) followed by taper.	Monitor changes of renal function
	Grade 3 or 4	Permanently discontinue		
Neurological Toxicities	Grade 2	Withhold	Based on severity of AE, administer corticosteroids	Ensure adequate evaluation to confirm etiology and/or exclude other causes
	Grade 3 or 4	Permanently discontinue		
Myocarditis	Asymptomatic cardiac enzyme elevation with	Withhold	Based on severity of AE, administer corticosteroids	Ensure adequate evaluation to confirm etiology and/or exclude other causes

Immune-related AEs	Toxicity grade or conditions (CTCAE v5.0)	Action with pembrolizumab	irAE management with corticosteroid and/or other therapies	Monitoring and follow-up
	clinical suspicion of myocarditis (previously CTCAE v4.0 Grade 1)			
Exfoliative Dermatologic Conditions	Grade 2, 3, or 4	Permanently discontinue		
	Suspected SJS, TEN, or DRESS	Withhold	Based on severity of AE, administer corticosteroids	Ensure adequate evaluation to confirm etiology and/or exclude other causes
	Confirmed SJS, TEN, or DRESS	Permanently discontinue		
All other irAEs	Persistent Grade 2	Withhold	Based on severity of AE, administer corticosteroids	Ensure adequate evaluation to confirm etiology and/or exclude other causes
	Grade 3	Withhold or discontinue based on the event ^e		
	Recurrent Grade 3 or Grade 4	Permanently discontinue		

AE(s)= adverse event(s); ALT=alanine aminotransferase; AST=aspartate aminotransferase; CTCAE=Common Terminology Criteria for Adverse Events; DRESS=Drug Rash with Eosinophilia and Systemic Symptom; GI=gastrointestinal; ir=immune related; IV=intravenous; SJS=Stevens-Johnson Syndrome; T1DM=Type 1 diabetes mellitus; TEN=Toxic Epidermal Necrolysis; ULN=upper limit of normal.

NOTE: Non-irAE will be managed as appropriate, following clinical practice recommendations.

^a AST/ALT: >3.0 to 5.0 x ULN if baseline normal; >3.0 to 5.0 x baseline if baseline abnormal;
bilirubin: >1.5 to 3.0 x ULN if baseline normal; >1.5 to 3.0 x baseline if baseline abnormal

^b AST/ALT: >5.0 to 20.0 x ULN, if baseline normal; >5.0 to 20.0 x baseline if baseline abnormal;
bilirubin: >3.0 to 10.0 x ULN if baseline normal; >3.0 to 10.0 x baseline if baseline abnormal

^c AST/ALT: >20.0 x ULN if baseline normal; >20.0 x baseline if baseline abnormal;
bilirubin: >10.0 x ULN if baseline normal; >10.0 x baseline if baseline abnormal

^d The decision to withhold or permanently discontinue pembrolizumab is at the discretion of the investigator or treating physician. If control achieved or \leq Grade 2, pembrolizumab may be resumed.

^e Events that require discontinuation include but are not limited to: encephalitis and other clinically important irAEs (eg, vasculitis and sclerosing cholangitis).

5.3.4.2. Dose Modification and Toxicity Management of Infusion Reactions Related to Pembrolizumab

Pembrolizumab may cause severe or life-threatening infusion-reactions including severe hypersensitivity or anaphylaxis. Signs and symptoms usually develop during or shortly after drug infusion and generally resolve completely within 24 hours of completion of infusion. Dose modification and toxicity management guidelines on pembrolizumab associated infusion reaction are provided in [Table 16](#).

Table 16 Pembrolizumab infusion reaction dose modification and treatment guidelines

NCI CTCAE Grade	Treatment	Premedication at Subsequent Dosing
Grade 1 Mild reaction; infusion interruption not indicated; intervention not indicated	Increase monitoring of vital signs as medically indicated until the patient is deemed medically stable in the opinion of the investigator.	None
Grade 2 Requires therapy or infusion interruption but responds promptly to symptomatic treatment (eg, antihistamines, NSAIDs, narcotics, IV fluids); prophylactic medications indicated for ≤24 hrs.	
Stop Infusion.
 
Additional appropriate medical therapy may include but is not limited to:
 
 IV fluids Antihistamines NSAIDs Acetaminophen Narcotics 
Increase monitoring of vital signs as medically indicated until the patient is deemed medically stable in the opinion of the investigator.
 
If symptoms resolve within 1 hour of stopping drug infusion, the infusion may be restarted at 50% of the original infusion rate (eg, from 100 mL/hr to 50 mL/hr). Otherwise, dosing will be held until symptoms resolve and the patient should be premedicated for the next scheduled dose.
 
Patients who develop Grade 2 toxicity despite adequate premedication should be permanently discontinued from further study drug treatment.
	
Patient may be premedicated 1.5 h (±30 minutes) prior to infusion of pembrolizumab with:
 
Diphenhydramine 50 mg po (or equivalent dose of antihistamine).
 
Acetaminophen 500–1000 mg po (or equivalent dose of analgesic).

Grades 3 or 4 Grade 3: Prolonged (i.e., not rapidly responsive to symptomatic medication and/or brief interruption of infusion); recurrence of symptoms following initial improvement; hospitalization indicated for other clinical sequelae (eg, renal	
Stop Infusion.
 
Additional appropriate medical therapy may include but is not limited to:
 
 Epinephrine** IV fluids Antihistamines NSAIDs Acetaminophen Narcotics Oxygen 	No subsequent dosing

NCI CTCAE Grade	Treatment	Premedication at Subsequent Dosing
impairment, pulmonary infiltrates) Grade 4: Life-threatening; pressor or ventilator support indicated	
 • Pressors • Corticosteroids 
Increase monitoring of vital signs as medically indicated until the patient is deemed medically stable in the opinion of the investigator.
 
Hospitalization may be indicated.
 
**In cases of anaphylaxis, epinephrine should be used immediately.
 
Subject is permanently discontinued from further study drug treatment.
	

Appropriate resuscitation equipment should be available at the bedside and a physician readily available during the period of drug administration.

For further information, please refer to the Common Terminology Criteria for Adverse Events v5.0 (CTCAE) at <http://ctep.cancer.gov>

5.3.4.3. Other Allowed Dose Interruption for Pembrolizumab

Pembrolizumab may be interrupted for situations other than treatment-related AEs such as medical/surgical events or unforeseen circumstances not related to study therapy. Patients should be placed back on study therapy within 3 weeks of the originally scheduled dose and within 42 days of the previously administered dose, unless otherwise discussed with the sponsor. The reason for interruption should be documented in the patient's study record.

Patients who discontinue LV due to an LV-related AE (see Sections 5.2.4.2 and 5.2.4.3) may continue pembrolizumab with approval of the medical monitor if there is evidence of clinical benefit. The maximum allowed number of pembrolizumab cycles is 35 (approximately 2 years).

5.3.5. Storage and Handling

Pembrolizumab should be stored and handled per the pharmacy manual.

5.3.6. Packaging and Labeling

Pembrolizumab is commercially available in the US.

5.3.7. Preparation

Pembrolizumab should be prepared per the pharmacy manual.

5.4. Concomitant Therapy

All concomitant medications, blood products, and radiotherapy administered will be recorded from Day 1 (predose) through the safety reporting period. Any concomitant medication given for a study protocol-related AE should be recorded from the time of informed consent.

5.4.1. Required Concomitant Therapy

G-CSF is required in the following situations.

- Part A: Subjects who experience Grade 4 neutropenia or febrile neutropenia (any grade) in any cycle with LV treatment must receive G-CSF treatment during the cycle, and must receive prophylactic G-CSF for all subsequent cycles.
- Part A: Subjects weighing over 80 kg and receiving >200 mg per infusion of LV in a cycle must be given prophylactic G-CSF, starting with their first dose of >200 mg per infusion. Once a subject receives G-CSF, it is strongly recommended that G-CSF continue to be administered to that subject at each subsequent cycle, regardless of weight change or LV dose, if it is deemed to be needed per investigator's clinical judgment.
- In Part B and Part C, primary prophylactic G-CSF is not required but is allowed (see Section [5.4.2 Allowed Concomitant Therapy](#) and Section [5.4.3. Myeloid Growth Factors](#)).

The administration of G-CSF should be consistent with American Society of Clinical Oncology (ASCO) guidelines ([Smith 2015](#)) ([Appendix G](#)).

- Prophylactic G-CSF should start 1 to 3 days after LV administration.
- G-CSF (including pegfilgrastim) should not be given within 24 hours prior to the dose of LV.
- If pegfilgrastim is used, a one-time dose per cycle is recommended.
- If daily G-CSF for treatment of AEs is used, treat for at least 5 to 7 days, or until the ANC is >1000/mm³ (\leq Grade 2).

If the subject is taking chronic suppressive or prophylactic anti-infectives (antiviral, antifungal, or antibacterial), documentation of investigations to ensure the absence of active infection must be completed prior to enrollment. The subject should continue suppressive or prophylactic anti-infectives for the duration of study participation.

5.4.2. Allowed Concomitant Therapy

The use of antibiotics including prophylactics, when applicable, is allowed. Subjects who are receiving P-glycoprotein (P-gp) or strong cytochrome P450 3A (CYP3A) inhibitors concomitantly with LV should be closely monitored for adverse reactions. Based upon evaluation of the anti-CD30 MMAE ADC brentuximab vedotin (ADCETRIS Prescribing Information, Seagen, Inc., Oct 2019), concomitant use of P-gp inhibitors or strong CYP3A4 inhibitors has the potential to increase the exposure to MMAE (the cytotoxic component of LV and brentuximab vedotin). Concomitant use of P-gp inducers or strong CYP3A4 inducers could decrease exposure to MMAE. See [Appendix F](#) for a list of P-gp and CYP3A inducers and inhibitors.

Therapy with bisphosphonates or other fracture prophylaxis agents are permitted.

5.4.2.1. Blood Product Transfusions

Transfusions of blood products may be administered according to institutional standards.

5.4.2.2. Premedication

Routine premedication for infusion reactions should not be administered prior to the first dose of LV. However, subjects who experience IRRs may receive subsequent treatment with premedication. The use of intermittent high-dose corticosteroid treatment of >20 mg/day to prevent or manage hypersensitivity reactions, or other noncancer related symptoms, is allowed. For the management of infusion reactions, including recommended concomitant therapy, see Section 5.5.1.

5.4.2.3. Radiotherapy

Palliative radiotherapy (eg, treatment for stable symptomatic, non-target solitary lesion) may be considered on an exceptional case-by-case basis after consultation with the medical monitor, provided it does not interfere with assessment of tumor response per RECIST v1.1, put the subject at risk for increased or worsened AEs, and is not being used to treat PD. Palliative radiotherapy should be given no sooner than 2 weeks before or 2 weeks after treatment with LV.

5.4.2.4. Supportive Care Medications

It is recommended that subjects receive treatment for constipation, nausea, vomiting, or other gastrointestinal signs or symptoms.

Although not required, subjects should be up-to-date on any recommended vaccinations prior to study entry. Seasonal inactivated (non-live) influenza vaccine is allowed.

5.4.3. Myeloid Growth Factors

See Section 5.4.1 and Appendix G. Subjects in any cohort of the study may receive G-CSF as clinically indicated.

Myeloid growth factors (including pegfilgrastim) **should not be given** within 24 hours prior to any dose of LV.

For subjects enrolled in Part B and C, long-acting myeloid growth factors (such as pegfilgrastim) may not be appropriate when LV is given weekly. Long-acting myeloid growth factors should only be given when there is sufficient time for the growth factors to have cleared and for growth stimulatory activity to have ceased. In addition, adherence to the 2015 ASCO guideline for the use of white blood cell growth factors is recommended for the management and/or prophylaxis of neutropenia and febrile neutropenia (Smith 2015).

5.4.4. Prohibited Concomitant Therapy

No other investigational drug, immunosuppressive medication, non-study systemic antineoplastic therapy, or approved anticancer treatment is permitted during the treatment period, including chemotherapy, endocrine therapy, biological response modifiers, surgery, immunotherapy, or radiotherapy (except palliative radiotherapy, see Section 5.4.2.3). Concurrent participation in another clinical trial of a medical intervention is not allowed.

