4. STUDY POPULATION

Subjects must meet all enrollment criteria to be eligible for this study. Eligibility criteria may not be waived by the investigator and are subject to review in the event of a good clinical practice audit and/or health regulatory authority inspection.

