- Cohort 6, gastric and GEJ adenocarcinoma (Part A and Part B):
 - Must have pathologically-documented gastric or GEJ adenocarcinoma;
 - Must have unresectable locally advanced or metastatic disease;
 - Must have received prior platinum-based therapy;
 - Must have disease progression during or following systemic therapy;
 - Subjects with known human epidermal growth factor receptor 2 (HER2) overexpression must have received prior HER2-targeted therapy;
 - No more than 1 line of prior cytotoxic chemotherapy for their advanced disease;
 - Subjects may have received prior anti-PD(L)1 therapy, unless contraindicated.
- Cohort 7, CRPC (Part B only):
 - Must have histologically or cytologically confirmed adenocarcinoma of the prostate:
 - Subjects with components of small cell or neuroendocrine histology are excluded.
 - Must have metastatic castration-resistant disease:
 - Castration-resistant is defined as progressive disease following adequate medical or surgical (bilateral orchiectomy) castration and testosterone <50 ng/dL (<2.0 nM).
 - Must have been ≥28 days between cessation of androgen receptor-targeted therapy and start of study treatment;
 - Must have received no more than 1 prior line of 2nd generation androgen receptor-targeted therapy (eg, abiraterone acetate, enzalutamide, apalutamide,

- or darolutamide) for metastatic castration-sensitive prostate cancer (CSPC) or CRPC;
- No prior cytotoxic chemotherapy in the metastatic CRPC setting:
 - For subjects who received cytotoxic chemotherapy for CSPC, at least 6 months must have elapsed between last dose of chemotherapy and start of study treatment;
 - No more than 1 prior line of cytotoxic chemotherapy for CSPC
- Subjects with measurable and non-measurable disease are eligible if the following criteria are met:
 - A minimum starting PSA level ≥ 1.0 ng/mL;
 - Subjects with measurable soft tissue disease must have evidence of measurable soft tissue disease according to PCWG3 criteria. Previously normal (<1.0 cm) lymph nodes must have grown by ≥ 5 mm in the short axis to be considered to have progressed;
 - Subjects with nonmeasurable- disease (enrollment after interim analysis and no more than 15 subjects in total) must have documented rising PSA levels or appearance of new lesion according to PCWG3 ([Appendix L](#)):

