4.2. Exclusion Criteria

Parts A, B, and C

1. Subjects with active concurrent malignancy or a previous malignancy within the past 3 years are excluded. Exceptions are malignancies with a negligible risk of metastasis or death (eg, 5-year OS $\geq 90\%$), such as adequately treated carcinoma in situ of the cervix, non-melanoma skin carcinoma, localized prostate cancer, ductal carcinoma in situ, or Stage I uterine cancer, and does not interfere with the evaluation of the study therapy efficacy or safety.
2. Any anticancer therapy (such as cytotoxic chemotherapy, biologic therapy, immunotherapy etc.) within 3 weeks of starting study treatment. Subjects who are/were on adjuvant hormonal therapy for the treatment of malignancies with negligible risk of metastases (as described in exclusion criteria 1) are eligible.
3. Subjects with known active central nervous system (CNS) lesions (including leptomeningeal metastasis) are excluded. Subjects with symptoms concerning for active CNS disease must have been evaluated and treated per institutional standard of care. Subjects with definitively treated brain metastasis (surgery and/or radiotherapy) are eligible if they meet the following criteria:
 - Asymptomatic from the CNS metastases
 - Completely off steroids; anti-convulsants at a stable dose are allowed.
 - No evidence of clinical and radiographic disease progression in the CNS for ≥ 3 weeks after definitive radiotherapy and/or surgery
4. Active viral, bacterial, or fungal infection requiring systemic treatment within 7 days prior to the first dose of LV. Routine antimicrobial prophylaxis is permitted.
5. Subjects with any ongoing clinically significant toxicity (Grade 2 or higher, per the NCI CTCAE, v5.0) associated with prior treatment (including systemic therapy, radiotherapy, or surgery) are not permitted (except alopecia).
6. Ongoing sensory or motor neuropathy of Grade ≥ 2
7. Subjects with known and untreated hepatitis B, hepatitis C, or human immunodeficiency virus (HIV). Subjects are eligible if they are on a stable anti-viral treatment or have received curative therapy (check [Appendix F](#) for a list of drug-drug interactions).
 - **Part C Arm 2 and Arm 3 only:**
 - HIV+ subjects with a history of Kaposi sarcoma and/or Multicentric Castleman Disease are not eligible.
 - HIV+ subjects on anti-retroviral therapy (ART) must meet the following criteria to be eligible:
 - CD4+ T-cell count >350 cells/mm³ at time of screening

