 - Confirmed HIV RNA level below 50 copies/ml or the lower limit of qualification (below the limit of detection) using the locally available assay at the time of screening and for at least 12 weeks prior to screening

- Stable ART regimen with no changes in drugs or dose modification for at least 4 weeks prior to study entry (Day 1)

8. Current therapy with other systemic antineoplastic or investigational agents
9. Subjects who are breastfeeding, pregnant, or planning to become pregnant from time of informed consent until 6 months after the final LV administration
10. Known hypersensitivity to any excipient contained in the drug formulation of LV (all Parts) or pembrolizumab (Part C only).
11. Documented history of a cerebral vascular event (stroke or transient ischemic attack), unstable angina, myocardial infarction, or cardiac symptoms consistent with congestive heart failure, Class III-IV, by New York Heart Association criteria within 6 months prior to study enrollment ([Appendix E](#)).
12. Has received prior radiotherapy within 2 weeks of start of study treatment. A subject is also excluded if radiotherapy occurred more than 2 weeks prior to start of study treatment but the subject has not recovered from radiation-related toxicities, requires corticosteroids, or has had radiation pneumonitis.
13. Other serious or uncontrolled underlying medical condition that, in the opinion of the investigator, would impair the subject's ability to receive or tolerate the planned treatment and follow-up (eg, active cardiac disease, active systemic infection, chronic conditions, any psychiatric or substance abuse disorders), interfere with the subject's cooperation with the requirements of the trial, place the subject at undue risk of SAE, or make the subject unable to receive sustained therapy
14. Has received a live vaccine within 30 days of the planned start of study therapy. Seasonal influenza vaccines for injection are generally inactivated and are allowed; however, intranasal influenza vaccines (eg, Flu-Mist) are live attenuated vaccines and are not allowed.

Part C Only

15. Has received prior therapy with an anti-PD-1, anti-PD-L1, or anti-PD-L2 agent or with an agent directed to another stimulatory or co-inhibitory T-cell receptor (eg CTLA-4, OX 40, CD137), and was discontinued from that treatment due to a Grade 3 or higher immune-related adverse event (irAE).

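### Section 5.4.4 bars endocrine therapy with no exception for the medical castration that the prostate cancer cohort (Cohort 7) admits, so PSA response and ORR could be measured on a changed or mixed hormonal background

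*Protocol*

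**What the plan says.** **The prohibition.** Section 5.4.4 (Prohibited Concomitant Therapy) states that no "approved anticancer treatment is permitted during the treatment period, including chemotherapy, endocrine therapy, biological response modifiers". It is not limited to particular cohorts, and the one exception is palliative radiotherapy.

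**Cohort 7 entry.** Section 4.1 defines castration resistance as "progressive disease following adequate medical or surgical (bilateral orchiectomy) castration and testosterone <50 ng/dL". It also requires at least 28 days "between cessation of androgen receptor-targeted therapy and start of study treatment". Subjects with nonmeasurable disease may join, subject to a limit: "enrollment after interim analysis and no more than 15 subjects in total".

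**Eligibility rules that bear on it.** Exclusion 2 in Section 4.2 bars anticancer therapy in the 3 weeks before study treatment. Its hormonal exemption reads "Subjects who are/were on adjuvant hormonal therapy for the treatment of malignancies with negligible risk of metastases". Exclusion 8 bars "Current therapy with other systemic antineoplastic or investigational agents". Section 4 adds: "Eligibility criteria may not be waived by the investigator".

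**Allowed therapy.** Section 5.4.2, where an allowance would be expected, says "Therapy with bisphosphonates or other fracture prophylaxis agents are permitted" and does not mention castration.

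**Endpoints and monitoring.** Section 9.3.5.1 makes confirmed PSA response a primary endpoint for prostate cancer in addition to ORR. Table 7 lists PSA-DOR and PSA-PFS as secondary. Section 7.6.3 schedules testosterone at screening only.

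**The concern.** For a subject castrated by drug, castration is endocrine therapy. Section 5.4.4 therefore forbids, during treatment, what maintains the hormonal state that Section 4.1 requires at entry. Read literally, a site must stop medical castration, exclude the subject, or continue it and deviate from the protocol. Section 10.3.2 makes deviations reportable to the sponsor and to the ethics committee in line with that committee's policies.

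Sites may resolve this differently. Cohort 7 is single-arm, so no control group would absorb a change in hormonal background. Where castration was stopped near or after the first dose, a change in PSA or in tumor size could not be credited to LV alone. The two primary endpoints and the PSA-based secondary endpoints would all be affected, and no planned analysis separates these subjects.

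**Working it through.** The plan states no figure on this point that could be wrong, so the main check is of the text.

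**1. Is there an exemption for ongoing castration?**

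| Place | What it does | Settles the question? |
|---|---|---|
| 4.1, Cohort 7 | Defines castration resistance at entry; 28-day washout for androgen receptor-targeted agents only | No. Suggests castration continues but does not say so |
| 4.2, exclusion 2 | Bars recent anticancer therapy; hormonal exemption only for other, negligible-risk malignancies | No. Hormonal therapy is not named as barred, so its reach is unclear |
| 4.2, exclusion 8 | Bars current systemic antineoplastic agents | No exemption |
| 5.4.1 to 5.4.3 | Growth factors, bone agents, transfusion, premedication, radiotherapy, supportive care | Silent |
| 5.4.4 | Bars endocrine therapy; excepts palliative radiotherapy | This is the conflict |
| 6.3, 7.2, Appendices C and L | Prostate visits, PSA and imaging rules | Silent |
| SAP | Written for the original protocol; six cohorts, no CRPC | Silent |

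No exemption exists, and no text orders castration to be stopped.

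**2. Could the data show who was affected?** Section 5.4 records concomitant medications from Day 1 predose, so on-treatment stops would appear. Earlier stops would have to come from the medical history and prior treatment in Section 7.1. Castrate status after screening is not verified, because testosterone is not repeated.

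**3. Outer bounds (Sections 9.1 and 4.1).**
- Cohort 7 share of planned enrolment: 30 / 414 = 7.2%, less subjects with bilateral orchiectomy.
- Cap on nonmeasurable disease: 15 / 30 = 50% of the cohort. Appendix H defines partial response on target lesions, so for these subjects the primary readout rests mainly on PSA.

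**4. How few subjects could matter.** In Table 20, moving from 3 to 4 responses among the first 12 CRPC subjects raises the predictive probability of success (PPoS) from 6% to 21%, across the 10% futility line. That table counts CR and PR, so this concerns tumor response. The plan states no prior. With a Beta(0.3, 0.7) prior, my values for 3 and 4 responses are 5.2% and 19.9%. The cut-off of 3 or fewer of 12 also holds with Beta(0.2, 0.8), Beta(0.5, 0.5) and Beta(1, 1).

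The following is an illustration, not an estimate. Assume a true response rate *p* on maintained castration, and a share *s* of subjects who stop castration and cannot respond. The effective rate is *q* = *p*(1 − *s*), and the chance of passing the interim is P(X ≥ 4) with X ~ Bin(12, *q*):

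| *s* | *p* = 0.30 | *p* = 0.40 | *p* = 0.50 |
|---|---|---|---|
| 0% | 0.507 | 0.775 | 0.927 |
| 10% | 0.414 | 0.680 | 0.866 |
| 25% | 0.276 | 0.507 | 0.718 |
| 50% | 0.092 | 0.205 | 0.351 |

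Neither *p* nor *s* is in the documents, and assuming no response in those who stop is an extreme case.

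**The case against.** The best counter-argument is that the Cohort 7 criteria already show the intent. If all endocrine therapy had to stop, there would be little reason to set a washout for androgen receptor-targeted agents alone. Section 5.4.4 is a generic paragraph, and a site treating castration-resistant disease may well keep castration going whatever it says. Testosterone below 50 ng/dL is part of the entry definition, so subjects start from a comparable state. Exclusions 2 and 8 do not name hormonal therapy, and reading exclusion 8 to bar castration would shut out subjects whom Section 4.1 admits. The harm is conditional, and the bias has neither a known size nor a known direction. Part of it could be detected from the medication listings, and exploratory subgroup analyses are allowed.

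Much of this stands. The intent was probably to continue castration, the eligibility limb is weaker than Section 5.4.4, and no effect size can be claimed. But inferred intent does not lift an express prohibition. A site that relies on it is outside the written protocol, and a site that complies changes the hormonal background. The narrow exemption in exclusion 2 makes matters worse, because it implies that other hormonal therapy counts as anticancer therapy. The permitted subgroup analyses are optional, and the list in SAP Section 5.8 does not include castration status.

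**Conclusion.** The concern holds. As written, Section 5.4.4 prohibits a background therapy that many Cohort 7 subjects may be receiving, and nothing in the protocol or SAP exempts it. It should be fixed.

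Confidence is high on the textual conflict. The effect on results is conditional on how sites read the rule and on how many subjects are castrated medically, and the documents give neither. The firm bounds are up to 30 of about 414 subjects (7%), less those with orchiectomy, and up to 15 of those 30 (50%) with nonmeasurable disease, for whom PSA carries most of the primary readout.

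**What to change.** - **Protocol wording.** In Section 5.4.4 and in exclusions 2 and 8 of Section 4.2, state that Cohort 7 subjects without bilateral orchiectomy continue their ongoing medical castration at entry and throughout treatment. Keep the 28-day washout for androgen receptor-targeted agents.
- **Analysis.** Flag Cohort 7 subjects whose castration therapy was stopped or changed, using medical history and prior treatment (Section 7.1) before the first dose and concomitant medications (Section 5.4) from Day 1. Show confirmed PSA response rate, PSA-DOR, PSA-PFS and ORR with and without them. Keep this descriptive, since few subjects may be flagged.

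The cost is one wording amendment and one extra Cohort 7 tabulation, with no added visits, tests or subjects. On-study testosterone would still go unverified. Repeating it at existing visits would close that gap at the price of an added test, but the amendment does not depend on it.
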